8.3.2. Subject Enrollment and Disposition

The number (%) of subjects who completed or discontinued the study and reasons for early discontinuation will be summarized by treatment for subjects in the ITT population.

8.3.3. Demographics and Baseline Characteristics

Demographics and baseline characteristics will be summarized for subjects in the ITT population.

8.3.4. Efficacy Analyses

The analyses of the efficacy endpoints will be based on subjects in the ITT population.

8.3.4.1. Analysis of Primary Endpoint Change in PUL from Baseline to Week 52

The primary endpoint, Change in the total score of Performance of Upper Limb [(PUL) 2.0 version], from baseline to Week 52 will be analyzed using a random coefficient model with treatment, visit, visit-by-treatment interaction, , and baseline total score of Performance of Upper Limb value as fixed effects; the intercept and linear slope of visit as random effects. The primary analysis will be based on observed data from subjects in the ITT population.

As sensitivity analysis, the analysis of covariance model (ANCOVA) model with Multiple Imputations (ANCOVA –MI) will be also applied. The model will include treatment and baseline total score of Performance of Upper Limb value. The primary analysis will be based on the ITT population.

PUL 2.0 scale:

- The PUL 2.0 scale, total score = 42.
- High Level: Shoulder Dimension, 6 items: Max score = 12
- Mid-level: Elbow Dimension, 9 items: Max score = 17
- Distal level: Wrist and Finger Dimension, 7 items: Max score = 13

8.3.4.2. Analyses of Secondary Endpoints

Changes in ppFVC and ppPEF from Baseline to Week 52

The Change from baseline to Week 52 in ppFVC will be analyzed using a random coefficient model with treatment, visit, visit-by-treatment interaction, and baseline ppFVC as fixed effects; the intercept and linear slope of visit as random effects. The analysis will be based on observed data from subjects in the ITT population.

The Change from baseline to Week 52 in ppPEF will be analyzed using a random coefficient model with treatment, visit, visit-by-treatment interaction, and baseline ppPEF as fixed effects; the intercept and linear slope of visit as random effects. The analysis will be based on observed data from subjects in the ITT population.

Change in the Grip Strength of the Hands from baseline to Week 52, assessed by Hand Held Myometry (HHM)

The Change from baseline to Week 52 in grip strength of the hands will be analyzed using a random coefficient model with treatment, visit, visit-by-treatment interaction, and baseline value as fixed effects; the intercept and linear slope of visit as random effects. The analysis will be based on observed data from subjects in the ITT population.

Change in Left Ventricular Ejection Fraction percentage (LVEF %) from Baseline to Week 52, Assessed by MRI.

Summary of Listing and the analyses of the change from baseline to week 52 in LVEF (%) assessed by MRI will be conducted in the ITT population.

The change from baseline to Week 52 in left ventricular ejection fraction percentage (LVEF%), as assessed by MRI will be analyzed using a random coefficient model with treatment, visit, visit-by-treatment interaction, and baseline value as fixed effects; the intercept and linear slope of visit as random effects.

As an exploratory endpoint, the dichotomous responder (proportion of patients with change from baseline in LVEF% ≥ 0 at Week 52) will be summarized and analyzed. The logistic regression model will be used to compare the proportion of subjects with change from baseline in LVEF% ≥ 0 . The model will include treatment and baseline LVEF%.

For other secondary endpoints, MMRM model will be used in continuous variables; logistic regression model in binary variables; Cox regression model in time-to-event variables. The analysis models will include appropriate baseline factors. Other methods will be applied as appropriate.

Detailed analyses of all secondary endpoints will be clearly outlined in the SAP.

8.3.5. Exploratory analysis:**Change in the subscores of three regional dimensions (High-level (shoulder), Mid-level (elbow), Distal-level (wrist and hand)) of PUL, from baseline to Week 52**

Summary of the listings and analyses of subscores of three regional dimensions (High-level (shoulder), Mid-level (elbow), Distal-level (wrist and hand)) of PUL will be summarized for subjects in the ITT population.

The change from baseline to Week 52 in subscores of three regional dimensions (High-level (shoulder), Mid-level (elbow), Distal-level (wrist and hand)) of PUL will be analyzed using the Mixed Model for Repeated Measure (MMRM) with treatment, visit, treatment-visit interaction, and baseline endpoint value as fixed effects, with an unstructured variance - covariance matrix.

Changes in Cardiac Fibrosis Score from Baseline to Week 52, Assessed by Late Gadolinium Enhancement (LGE).

Summary of the listings and analyses of changes in cardiac fibrosis (LGE) will be based on the ITT population.

The change from baseline to Week 52 in cardiac fibrosis score assessed by MRI and Mass of Late Gadolinium Enhancement (Scar Mass), will be analyzed using the Mixed Model for

Repeated Measure (MMRM) with treatment, visit, treatment-visit interaction, and baseline endpoint value as fixed effects, with an unstructured variance - covariance matrix.

In addition, dichotomous responder analysis (proportion of patients with change from baseline in cardiac fibrosis score ≤ 0 at Week 52) will be summarized and analyzed. The logistic regression model will be used to compare the proportion of subjects with change from baseline in cardiac fibrosis ≥ 0 . The model will include treatment and baseline cardiac fibrosis score.

Change in Myocardial Circumferential Strain [Global Circumferential Strain (GCS)%] percentage from Baseline to Week 52, Assessed by cardiac MRI.

Summary of the listings and analyses of annual changes from baseline for the Global Myocardial Circumferential Strain (GCS) will be summarized for subjects in the ITT population,

The change from baseline to Week 52 in GCS score will be analyzed using the Mixed Model for Repeated Measure (MMRM) with treatment, visit, treatment-visit interaction, and baseline endpoint value as fixed effects, with an unstructured variance - covariance matrix

In addition, dichotomous responder analysis (proportion of patients with change from baseline in GCS score ≥ 0 at Week 52) will be summarized and analyzed. The logistic regression model will be used to compare the proportion of subjects with change from baseline in GCS score ≥ 0 . The model will include treatment and baseline cardiac fibrosis score.

Changes in Fibrosis Score of the Biceps Brachii from Baseline to Week 52, Assessed by MRI

Summary of the listings and analyses of upper arm (bicep) muscle fibrosis assessed by MRI, will be summarized based on ITT population;

The change from baseline to Week 52 in fibrosis score of the biceps brachii muscle assessed by MRI will be analyzed using the Mixed Model for Repeated Measure (MMRM) with treatment, visit, treatment-visit interaction, and baseline endpoint value as fixed effects, with an unstructured variance - covariance matrix

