3.1.1.4. Exploratory Endpoints

- Change in the subscores of three regional dimensions (High-level (shoulder), Mid-level (elbow), Distal-level (wrist and hand)) of PUL, from baseline to Week 52
- Change in Duchenne Video Assessment severity percentage from baseline to Week 52.

- Change in percent predicted forced expiratory volume at 1 second (FEV1) from baseline to Week 52.
- Analysis of progression of dilated cardiomyopathy (DCM) by genetic analysis.

Fibrosis/MRI assessments:

- Changes in fibrosis score of the biceps brachii, from baseline to Week 52, assessed by MRI.
- Changes in Cardiac fibrosis score from baseline to Week 52, assessed by Late Gadolinium Enhancement (LGE).
- Change in Myocardial Circumferential Strain [Global Circumferential Strain (GCS)] percentage from baseline to Week 52, assessed by cardiac MRI.

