### 5.3.2. Baseline and Change from Baseline Definitions

Baseline is defined as the last available value obtained prior to the first dose of study drug (or randomization date if no infusion received) if not specified otherwise ([Section 5.5](#)). The acceptable value on Day 1 will be used to define the baseline values. Unscheduled visits will be considered for baseline.

Change from baseline will be calculated by subtracting the baseline value from the post-dose assessment for each subject.

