**6.6.3.6.2. Changes in Cardiac Fibrosis Score from Baseline to Week 52, Assessed by Late Gadolinium Enhancement (LGE).**

Summary of the listings and analyses of changes in cardiac fibrosis (LGE) will be based on the ITT population.

The change from baseline to Week 52 in cardiac fibrosis score assessed by MRI and Mass of Late Gadolinium Enhancement (Scar Mass) between two treatment arms, will be compared by ANCOVA. The ANCOVA model will contain terms for treatment and baseline measurements.

In addition, dichotomous responder analysis (proportion of patients with change from baseline in cardiac fibrosis score  $\geq 0$  at Week 52) will be summarized and analyzed. The logistic regression model will be used to compare the proportion of subjects with change from baseline in cardiac fibrosis  $\geq 0$ . The model will include treatment and baseline cardiac fibrosis score.

**6.6.3.7. Change in Myocardial Circumferential Strain [Global Circumferential Strain (GCS)%] percentage from Baseline to Week 52, Assessed by cardiac MRI.**

Summary of the listings and analyses of annual changes from baseline for the Global Myocardial Circumferential Strain (GCS) will be summarized for subjects in the ITT population,

The change from baseline to Week 52 in GCS score between two treatment arms will be compared by ANCOVA. The ANCOVA model will contain terms for treatment and baseline measurements.

In addition, dichotomous responder analysis (proportion of patients with change from baseline in GCS score  $\geq 0$  at Week 52) will be summarized and analyzed. The logistic regression model will

be used to compare the proportion of subjects with change from baseline in GCS score  $\geq 0$ . The model will include treatment and baseline cardiac fibrosis score.

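### The GCS responder is defined as change ≥ 0 with no sign convention; if GCS is recorded as signed (negative) strain, worsening subjects are labelled responders

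*Protocol*

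**What the plan says.** Both documents list as exploratory the "Change in Myocardial Circumferential Strain [Global Circumferential Strain (GCS)] percentage from baseline to Week 52, assessed by cardiac MRI". Protocol 8.3.5 supplements the continuous comparison with a "dichotomous responder analysis (proportion of patients with change from baseline in GCS score" as the measure; the criterion is "change from baseline in GCS score ≥ 0 at Week 52", and the arms are compared by logistic regression on that event. SAP 6.6.3.7 repeats the definition. It says that the logistic model will "be used to compare the proportion of subjects with change from baseline in GCS score" at or above zero.

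SAP 5.3.2 fixes the arithmetic: "Change from baseline will be calculated by subtracting the baseline value from the post-dose assessment for each subject". It takes no absolute value and makes no exception for GCS.

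GCS is called a percentage in some places and a score in others. No section of either document gives its sign, a typical value or the direction of improvement. Protocol 6.2.6 leaves MRI interpretation to a separate imaging charter.

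**The concern.** Strain is fractional change in length, and the myocardial circumference shortens in systole. In signed form circumferential strain is therefore negative, and it rises towards zero as contraction weakens. A change of zero or more then means unchanged or weaker contraction.

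The cut-off has the same form as the LVEF rule in Protocol 8.3.4.2, "the dichotomous responder (proportion of patients with change from baseline in LVEF% ≥ 0 at Week 52", where a higher value is better. Signed GCS runs the other way.

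The surrounding text suggests that directions were not checked when these paragraphs were written:

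- Protocol 8.3.5 first defines the cardiac fibrosis responder as "proportion of patients with change from baseline in cardiac fibrosis score ≤ 0 at Week 52", and in the next sentence models change ≥ 0. SAP 6.6.3.6.2 uses ≥ 0 in both sentences, although Protocol 2.6.7 treats a reduction in cardiac fibrosis as favourable.
- For the GCS responder model the Protocol states: "The model will include treatment and baseline cardiac fibrosis score". The SAP has the same covariate. Baseline GCS would be expected there. This is a separate matter, but it looks like text carried over from the fibrosis paragraph.

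At stake is a responder table whose meaning depends on an export convention that the plan does not state. Under the signed convention, a drug that preserves contraction would show fewer responders than placebo.

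**Working it through.** The plan gives no figure for GCS, so there is nothing of its own to reproduce. The check is of direction first, then of size under stated assumptions.

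**Direction.** Let D = Week 52 value − baseline value (SAP 5.3.2). The rule is: responder if D ≥ 0 (Protocol 8.3.5, SAP 6.6.3.7). The values below are illustrative.

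| Subject | Signed: D | Responder as written | Magnitude: D | Responder as written |
|---|---|---|---|---|
| Weaker, −15% to −13% | −13 − (−15) = +2 | yes | 13 − 15 = −2 | no |
| Stronger, −15% to −17% | −17 − (−15) = −2 | no | 17 − 15 = +2 | yes |

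The rule classifies correctly on the magnitude scale and in reverse on the signed scale.

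**Size.** These inputs are assumptions, since the documents contain no GCS values: D is normal with SD s, and mean worsening is w strain points.

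- Signed scale: P(D ≥ 0) = Φ(w/s).
- Magnitude scale: P(D ≥ 0) = Φ(−w/s) = 1 − Φ(w/s).
- Odds ratio = odds on pamrevlumab ÷ odds on placebo.

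Worked case, s = 2, w = 1.0 on placebo and 0 on pamrevlumab:

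- Signed: placebo Φ(0.5) = 0.691, pamrevlumab Φ(0) = 0.500. OR = (0.500/0.500) ÷ (0.691/0.309) = 0.45.
- Magnitude: placebo 0.309, pamrevlumab 0.500. OR = (0.500/0.500) ÷ (0.309/0.691) = 2.24.

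Odds ratios over a range (signed scale as written / correct direction), with worsening shown as placebo, pamrevlumab:

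| SD of change | 1.0, 0 | 1.0, 0.5 | 0.5, 0 | 2.0, 1.0 |
|---|---|---|---|---|
| 1.5 | 0.34 / 2.96 | 0.58 / 1.73 | 0.59 / 1.71 | 0.30 / 3.37 |
| 2 | 0.45 / 2.24 | 0.67 / 1.50 | 0.67 / 1.49 | 0.42 / 2.37 |
| 3 | 0.59 / 1.71 | 0.76 / 1.31 | 0.77 / 1.31 | 0.58 / 1.73 |

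The direction reverses in every cell. Only the size depends on the assumptions.

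**Effect on the test.** Apart from subjects with a change of exactly zero, D ≥ 0 and D ≤ 0 are complementary events. Swapping them changes the sign of the log odds ratio and leaves its standard error alone, so the p-value is essentially unchanged.

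**Agreement with the ANCOVA.** Both GCS analyses use the same D. In the worked case on the signed scale, the mean difference (pamrevlumab minus placebo) is 0 − 1.0 = −1.0, and the proportion with D ≥ 0 is also lower on pamrevlumab (0.500 against 0.691). The two results point the same way numerically.

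**The case against.** The strongest objection is that the documents never say GCS is recorded as a negative number. The sign comes from the general definition of strain. The imaging charter, or the separate table specifications mentioned in SAP Section 1, may set a magnitude convention. The match with the LVEF rule fits that reading as well as it fits a copying slip. This stands. A reader might infer that worsening subjects will certainly be counted as responders, but the documents support that only conditionally.

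A reader might also infer that the responder table would contradict the GCS ANCOVA. It would not, because both use the same change variable. What would be reversed is the responder label and any reading of the odds ratio that relies on it. Nothing is lost that relabelling could not recover.

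The analysis is also an add-on to an exploratory endpoint. It is absent from SAP Table 1, and no primary, secondary or safety result uses the cut-off. This stands too, and it limits the weight of the point.

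None of this removes the gap. A pre-specified responder rule should not depend on a convention left unstated, and choosing the direction after unblinding would be post hoc.

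**Conclusion.** The point holds in conditional form and is minor. The responder cut-off is given without a sign convention or a direction of improvement. If GCS is recorded as signed strain, worsening subjects are labelled responders and the odds ratio is inverted: about 0.30 to 0.77 where the correct direction gives 1.31 to 3.37. Those ranges rest on assumed normal changes, SDs of 1.5 to 3 and a real benefit of 0.5 or 1.0 strain points. If GCS is recorded as a magnitude, the rule is right as it stands. Reading the continuous GCS result also needs the sign convention, although that analysis does not use the cut-off.

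**What to change.** In SAP 6.6.3.7, before unblinding:

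- Define the GCS responder as change in |GCS| ≥ 0 at Week 52. This is equivalent to signed change ≤ 0 when both readings are negative, and it is correct under either export convention.
- Use that same event in the logistic model.
- State that a more negative signed GCS is improvement.

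List the change in SAP Section 7, which already records departures from the protocol. No protocol amendment is needed. The cost is a few sentences in a SAP amendment and no new data.

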8.3.6. Pharmacokinetic Analyses

A population PK analysis, as well as an exposure-response analysis, will be defined in a separate plan.

8.3.7. Safety Analyses

All treatment-emergent adverse events (TEAEs) will be summarized by treatment arm, including: TEAEs Grade ≥ 3 , treatment-emergent serious adverse events (TESAEs), deaths, and TEAEs leading to study or investigational product discontinuation.

Clinically significant changes from baseline in vital signs and laboratory tests will be summarized. Hypersensitivity/anaphylactic reactions will be monitored.

Additionally, the following safety analyses will be conducted:

- Number and percentage of subjects with bone fractures
- Ulna length measurements for indirect measure of annualized growth velocity (cm/year) for subjects under the age of 18

8.4. Statistical Analysis Plan

The Statistical Analysis Plan (SAP) will include detailed analysis methods, statistical models, definitions, missing data handling as well as other data handling rules. It will document additional exploratory endpoints that are not specified in the protocol. The SAP will be finalized prior to database lock and treatment unblinding.

9. QUALITY CONTROL AND QUALITY ASSURANCE

9.1. Data Quality Assurance

Quality assurance and quality control systems will be implemented and maintained with Standard Operating Procedures by the Sponsor and its designee(s), as appropriate, to ensure that this clinical study is conducted and data are generated, documented (recorded) and reported in compliance with the protocol, ICH E6 (GCP), and other applicable regulations.

This study will be monitored by the Sponsor or designee in accordance with GCP, and may be audited or reviewed by an independent Quality Assurance department, IRB/IEC, and/or regulatory authorities. This implies that monitors and auditors/inspectors will have the right to inspect the study sites at any time during and/or after completion of the study and will have direct access to data/source documents, including the subject's file. By participating in this study, Investigators agree to this requirement.

The purpose of trial monitoring is to verify the following:

- The rights and well-being of human subjects are protected.
- The reported data are accurate, complete, and verifiable from source documents.
- All data are collected, tracked, and submitted by the site to the Sponsor or designee, including unscheduled and missed assessments
- The reported data are reconciled across all data sources (e.g., laboratory, safety, IRT, clinical databases).
- The conduct of the trial is in compliance with the currently approved protocol/amendment(s), with GCP, and with the applicable regulatory requirement(s).

Measures will be undertaken to protect the confidentiality of records that could identify subjects, respecting the privacy and confidentiality rules in accordance with applicable regulatory requirements.

9.2. Audit and Inspection

Authorized representatives of the sponsor, a regulatory authority, and/or an IRB/IEC may visit the investigator site to perform audits or inspections, including source data verification and source documentation review. The Investigator will allow the sponsor auditor (or designee), regulatory authority or ethics committee representative to inspect the drug storage area, study drug stocks, drug accountability records, subject charts (e.g. medical records) and study source documents, and other records relative to study conduct.

The purpose of an audit or inspection is to systematically and independently examine all study-related activities and documents to determine whether these activities were conducted, and data were recorded, analyzed, and accurately reported according to the protocol, ICH GCP guidelines, and any applicable regulatory requirements.

The investigator must contact the sponsor, or its third party representative (CRO), immediately if notified by a regulatory authority of an inspection pertaining to this study.

10. ETHICS

10.1. Ethical Considerations

The study will be conducted in accordance with applicable regulatory requirements, the International Conference on Harmonisation (ICH) E6 Guideline for Good Clinical Practice (GCP), the Declaration of Helsinki, any other applicable regulatory requirements, and Institutional Review Board (IRB) or Independent Ethics Committee (IEC) requirements.

10.2. Communication with the Institutional Review Board or Independent Ethics Committee

This protocol, the Informed Consent Form, the Investigator's Brochure, and any information to be given to the subject must be submitted to a properly constituted IRB/IEC by the investigator for review and approved by the IRB/IEC before the study is initiated and before any investigational product is shipped to the investigator. In addition, any subject recruitment materials must be approved by the IRB/IEC before the material is used for subject recruitment.

The investigator is responsible for obtaining reapproval by the IRB/IEC annually or as required by the policies and procedures established by the IRB/IEC. Copies of the investigator's annual report and other required reports submitted to the IRB/IEC and copies of the IRB/IEC continuance of approval must be furnished to the Sponsor or designee. A copy of the signed FDA Form 1572 or other qualified investigator statement (as required) must also accompany the above approval letter provided to the Sponsor.

Investigators are also responsible for promptly informing the IRB/IEC of any protocol changes or amendments, changes to the Investigator's Brochure, and other safety-related communications from the Sponsor or its designee. Written documentation of IRB/IEC approval must be received before the amendment is implemented.

Investigators must maintain a list of appropriate qualified persons to whom the investigator has delegated significant trial-related duties and update the list as staff and their delegated responsibilities change.

10.3. Subject Information and Consent

Prior to participation in any study-specific procedures, the subject must sign (note: all references to "subject" in this section refers to the study subject or their legally acceptable representative) an IRB/IEC-approved written Informed Consent Form (ICF) in their native language. The approved written informed consent must adhere to all applicable laws in regards to the safety and confidentiality of the subjects. To obtain and document informed consent, the Investigator should comply with applicable regulations, and adhere to ICH GCP standards and the ethical principles in the Declaration of Helsinki (October 2008).

The language in the written information about the study should be as non-technical as practical and should be understandable to the subject. Before informed consent is obtained, the Investigator should provide the subject ample time and opportunity to inquire about the study and to decide whether or not to participate.

All questions about the study should be answered to the satisfaction of the subject. The written ICF should be signed and personally dated by the subject and the person who conducted the

informed consent discussion, with any additional signatures obtained as required by applicable local regulations and IRB/IEC requirements. Each subject will be informed that participation is voluntary and that he/she can withdraw from the study at any time. All subjects will receive a copy of the signed and dated ICF.

If there are any changes to the IRB/IEC approved ICF during the subjects' participation in the study, the revised ICF must receive the IRB/IEC's written approval before use and subjects must be re-consented to the revised version of the ICF, if/as required by the IRB/IEC.

Guidance for Clinical Teams: For studies conducted in the United States, each subject must provide his or her consent for the use and disclosure of personal health information under the

U.S. Health Insurance Portability and Accountability Act (HIPAA) regulations by signing a HIPAA Authorization Form. The HIPAA Authorization Form may be part of the ICF or may be a separate document. IRB review may or may not be required for the HIPAA Authorization Form according to study site policies.

